12.3 Planned Interim Analyses (if applicable)

No interim analyses are planned for this protocol.

12.3.1 Safety Review

No safety analyses are planned for this protocol.

12.3.2 Efficacy Review

No efficacy review is planned for this protocol.

12.4 Final Analysis Plan

Analysis Population: All analyses will be intent-to-treat, i.e., all participants who provide data at baseline will retain their original assignment regardless of the treatment received. All statistical tests will be evaluated using a two-tailed alpha level of .05 and will express precision using 95% confidence intervals.

Center Effects: The Primary analysis will account for variation between centers using a mixed effects model. The empirical Bayes estimate of center effects resulting from this model will be analyzed to assess the degree of heterogeneity between centers by assessing the magnitude of the variance of the random effects. This assessment will consist of a formal statistical test to determine if the variance of the random effect is greater than zero as well as an assessment of its estimated magnitude. If a clinically meaningful amount of variability between centers is detected, exploratory analyses will be conducted to attempt to identify covariates related to center effects including

geographic information, demographic information, and disease-related information. If these analyses identify meaningful subgroups among the centers, subgroups of sites will be created based on the potential for differential effectiveness. These subgroup analyses will be considered secondary and will be conducted in a manner identical to the primary analysis provided that the subgroups are of sufficient size to merit such an analysis. The specific data related to the characteristics of these subgroups, should they prove to exist, will be reported separately.

Primary Outcome Analysis: We will test the primary study hypothesis, which posits the AMXM intervention to be more effective than placebo in reducing periodontal probing depths, using a hierarchical linear model (HLM; aka mixed models, random coefficients regression). This analysis will account for the correlation between longitudinal observations within tooth site, within participants, and by practitioner, each of which can be represented within the model by a random intercept. The primary outcome measure, PD in mm, is effectively continuous, within a fixed range being necessarily positive and bounded above by the anatomy of the tooth in question. The model will include the fixed effect of time by using two dummy indicators representing re-evaluation at 6 weeks and final study visit at 12 months. The model will also include a binary indicator for arm (AMXM vs placebo) and an interaction between the indicators for time and study arm. Significance of either interaction term will represent a difference between the treatment and control arm at that timepoint, with the 6-week time representing efficacy and the 12-month time representing long-term efficacy/durability. No transformation of these variables is likely to be necessary.

It is not presently anticipated that boundary value problems or deviations in the residual distribution of the primary outcome will negatively impact the proposed analysis' operating characteristics due to the large size of the study. However, sensitivity of the analysis to these factors will be assessed using residual plots. In addition, potential site effects and the impact of any overly influential sites will be investigated by assessing the cluster-bootstrap stability of the analysis. Resampling analysis will be conducted stratified by person and site. The analysis will be conducted within each replication and the variability will be assessed in terms of statistical significance, clinically meaningful effect size, and the distribution of observed treatment effects. Any deviations impacting performance will be mitigated by modification of the primary analysis potentially to an approach utilizing the Huber-White sandwich estimator for the variance.

Analysis of Secondary Measures: The analysis of all secondary outcome measures will use similar hierarchical generalized linear models to those described in the primary analysis above. Analyses of all secondary measures enhance and further characterize any effect demonstrated by the primary endpoint as opposed to alternative efficacy measures. Therefore no adjustments for multiple comparisons are necessary nor planned.

For continuous outcome measures of CAL and OHIP-5 we will use the same analytical framework described for the primary outcome, consisting of a mixed effects linear model with random effects for site, patient and provider and fixed effects for time (indicators for 6-week, 12 months) and treatment including a treatment by time interaction. Significance of either interaction term will represent a difference between the treatment and control arm at that timepoint, with the 6-week time representing efficacy and the 12-month time representing long-term efficacy/durability. No transformation of these variables is likely to be necessary.

For the secondary binary outcomes of BOP and the presence of residual disease (tooth level), we will use the generalized extension of the HLM using a logit link and binomial family (aka multilevel logistic regression, random coefficients logistic regression). The terms included in the model will be identical to that described for the continuous outcomes above.

The secondary outcome of remission (participant level) differs from the others in that it is measured at the person level and that the model is not longitudinal given that there is no variability at baseline (i.e., all participants at baseline meet the criteria of this outcome as it is part of the inclusion criteria for participation). Thus, outcome will be evaluated using mixed effects logistic regression, with a random effect for provider and a fixed effect for treatment assignment. This will be conducted separately at reevaluation (6 weeks) and final study visit (12 months). A significant and positive term for arm would indicate an effect of the treatment.

Key Subgroup Analyses & Analyses by Sex, Race and Ethnicity: In order to determine whether any key differences exist by age, sex, or race and ethnicity, analyses of each outcome will be conducted to assess if differences in the intervention effect are to be expected. For our regression analyses, this will take the form of the addition of an interaction term between treatment and subgroup, with a significant p-value suggesting a statistically meaningful difference between the effects experienced by the subgroups. Any significant differences will be examined to determine whether they are of a clinically significant magnitude and comparison of intervention effects will be achieved by reporting intervention effects and their confidence intervals separately for each sex and

for each race/ethnicity group. Further, the raw data will be summarized using boxplots (continuous) or bar charts (binary), stratified by subgroup to visually represent key differences should any be found. These analyses are supported by our randomization scheme which should result in relative balance of treatment assignment across subgroups resulting in unbiased effect estimates.

We will also perform secondary evaluations of the primary outcome measure to assess whether there is effect modification based on age and periodontitis stage and grade, which are key variables associates with periodontitis.

The analysis will consider the following variables:

- Race/ethnicity: non-Hispanic White, non-Hispanic Black, Mexican American, Other Hispanic, Other Race
- Age: continuous variable
- Sex: male or female
- Periodontitis Stage: II, III
- Periodontitis Grade: A, B, C

To test these potential moderators, we will adapt the model described for the primary outcome to include the moderator and product of the moderator and arm in the third level of the model for predicting all level 1 terms. A significant omnibus test based on a contrast would provide support for effect modification. We will probe the nature of any significant interaction by examining the pairwise differences in differences of the change (i.e., moderator X arm X time) and by plotting these values to facilitate interpretation.

Sensitivity of the analysis to model misspecification and potential site (provider) effects will be investigated by assessing the cluster-bootstrap stability of the analysis. Any deviations impacting performance will be mitigated by modification of the primary analysis potentially to an approach utilizing the Huber-White sandwich estimator for the variance.

Missing data

For all patient participants, we will attempt to gather follow-up information and reasons for dropout regardless of protocol completion and censor at the point of drop out. PBRN studies routinely attempt to collect reasons for dropout. We will compare baseline data between those with and without missing data and examine whether there are variables that are related to missingness. For each independent variable in the data set, the degree of missingness will be assessed. For key independent variables (demographics, and variables directly relevant to the analyses outlined above), variables with missingness will be dealt with using multiple (greater than or equal to 10) imputation by

chained equations and an appropriate variance will be derived using Rubin's rules (Azur et al. 2011).

Missing outcome variables will not be imputed for analysis. If for a given outcome variable less than 5% of the observations are missing, the missing observations will be dropped. If more than 5% of the outcome variables are missing and the study is positive (demonstrates a benefit for the treatment group over the control), subsequent tipping point analyses will be conducted to determine the potential influence of the missingness on the analysis. Tipping point analyses are used to determine how contrary to the observed data the missing data would need to be in order to reverse the findings of the study. This analysis will be conducted by fitting a predictive model to the observed study data and then using a modified version of that model to impute missing outcomes under progressively increased pessimism until the positive effect observed in the study is countered. This gives the reader an idea of how extremely contrary the missing outcomes would need to be in order to have been influential.

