Data Collection & Analysis: Following randomization, practitioners will obtain periodontal clinical measurements and optional baseline plaque samples, and then proceed with the intervention; i.e., an antibiotic (or placebo) regimen will be initiated, and standard SRP will be performed. Changes in periodontal clinical and patient-reported outcomes (see protocol section 3 for description of outcome) will be assessed at re-evaluation (6 weeks + 3 weeks) and at the final study visit (12 months -2,+3 months; range is 10-15 months) post-intervention. Both disease-oriented clinical outcomes (probing depth changes, attachment level changes, bleeding on probing) and an abbreviated oral health-related quality of life patient-reported outcome (Oral Health Impact Profile-5 (OHIP-5)) will be assessed at all timepoints.

In terms of the dependent variables employed in the analyses, overall there are 5 recorded variables (PD, BoP, CAL, OHIP-5, and AE) and the rest of the variables are calculated from these variables. As discussed in section 3, reduction in diseased sites is a calculated variable from PD by PD≥ 5mm; the maximum probing depth per tooth will be recorded as ≥5 mm (yes/no). Further, the disease remission variable is defined as the number of study patient participants who have ≤4 sites with PD≥5mm (Feres et al. 2020). This variable is calculated from PD≥ 5mm as the patient participants that display ≤4 sites with PD≥ 5mm; this is a dichotomization from the summation of PD≥ 5mm within person. All analyses will be data-level, and changes in site-level dependent variables at each timepoint will be assessed using mixed models to account for the clustering of longitudinal observations (level1) within tooth site (level 2) within patient participants (level 3) and will include a random intercept to account for multi-practitioner effects. Additional information is detailed in section 12.

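### The first step towards centre subgroups for differential effectiveness rests on a random-intercept variance, which measures probing-depth level and not variation in the AMXM effect

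*Protocol*

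**What the plan says.** Protocol section 12.4, Center Effects, takes the random effects of the primary mixed model and uses them to "assess the degree of heterogeneity between centers by assessing the magnitude of the variance of the random effects". This includes a "formal statistical test to determine if the variance of the random effect is greater than zero", together with a look at the estimated size. If the variability between centres is clinically meaningful, exploratory analyses look for covariates related to it. If those identify meaningful groupings, "subgroups of sites will be created based on the potential for differential effectiveness". On the resulting analyses the section says: "These subgroup analyses will be considered secondary and will be conducted in a manner identical to the primary analysis", provided the subgroups are large enough.

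The primary model is defined under Primary Outcome Analysis in the same section. The clustering levels are longitudinal observations within tooth site, "within participants, and by practitioner, each of which can be represented within the model by a random intercept". Section 4.2 says the same of the mixed models: they "will include a random intercept to account for multi-practitioner effects". The treatment effect enters as fixed terms: "The model will also include a binary indicator for arm (AMXM vs placebo) and an interaction between the indicators for time and study arm". Time is coded by two indicators (6 weeks, 12 months), with baseline as reference.

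**The concern.** A practitioner random intercept is shared by both arms and all visits. It absorbs whatever makes one practitioner's recorded depths higher or lower overall: the severity of the patients, probing force, reading of the probe. Randomisation is 1:1 in small blocks within practitioner (section 5.4.1), so this level largely cancels from each practitioner's AMXM-placebo contrast. Its variance says little about whether the contrast itself differs between practitioners.

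Yet the end of the sequence concerns differential effectiveness. The quantity that starts the search and the quantity the search is about are different. Level differences could start it when AMXM works equally everywhere, and the variance would not report how much the effect varies. This matters because the stated rationale (sections 2.1 and 2.2) is to learn where adjunctive antibiotics help.

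**Working it through.** The protocol gives no figure for this step, so there is nothing to reproduce. The structural argument comes from the text; the arithmetic shows direction and rough size.

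**Structure.** Center Effects refers to the random effects of the primary model. Primary Outcome Analysis and section 4.2 make the practitioner term an intercept. The arm-by-time effect is fixed, with one common value for all practitioners. No practitioner-level treatment slope and no practitioner-by-arm term is stated. The interaction tests under Key Subgroup Analyses cover age, sex, race/ethnicity, stage and grade, not centre. The cluster bootstrap checks stability and influential sites; it does not estimate the between-practitioner variance of the effect.

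**Inputs from the protocol.** 34 practitioners x 16 patients = 544; 1:1 allocation; target difference 0.2 mm; 220 per arm for 90% power; alpha 0.05; 20% dropout (sections 5.4, 12.2, 12.4).

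**Back-solved.** Patient-level SD of mean change: σc = 0.2 / [(1.960 + 1.282) x √(2/220)] = 0.647 mm, so σc² = 0.419.

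**Assumed, not in the protocol.** Between-patient SD of mean baseline depth σb = 0.4 to 0.8 mm; correlation 0.5 between the 6-week and 12-month changes; practitioner level SD τ and effect SD ω as listed, with the same effect at both follow-up visits.

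**Intercept test.** Average each patient's depth over the three visits. Within-practitioner variance is s² = σb² + σc²(2 + 2 x 0.5)/9 = σb² + σc²/3, which is 0.300 at σb = 0.4 and 0.780 at σb = 0.8. The practitioner F test has 33 and 509 df (5% critical value 1.459). Level differences inflate F by 1 + 16τ²/s².
- τ = 0.2: inflation 1 + 0.64/0.300 = 3.14 down to 1 + 0.64/0.780 = 1.82, so P(F > 1.459/inflation) is 99.6% down to 78%.
- An effect SD ω reaches half the patients at two of three visits, so it moves the practitioner mean by only ω x 1/2 x 2/3 = ω/3. At ω = 0.2 that is 0.067 mm.

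**Practitioner-by-arm test on 12-month change.** The variance of one practitioner's arm difference is ω² + 4σc²/n. With n = 16, 4 x 0.419/16 = 0.105; at ω = 0.2 the inflation is 1 + 0.04/0.105 = 1.38 and power is about 38%. With 6 per arm (n = 12; 16 x 0.8 = 12.8), 4 x 0.419/12 = 0.140; the inflation is 1.29 and power about 28%.

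**Results (percentage of trials with a significant test; simulation with 4000 runs per scenario agrees with these formulas to within simulation error)**

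| Level SD τ (mm) | Effect SD ω (mm) | Intercept test | Practitioner-by-arm test |
|---|---|---|---|
| 0.1 | 0 | 20 to 55 | about 5 |
| 0.2 | 0 | 78 to 99.6 | about 5 |
| 0.3 | 0 | 99 to 100 | about 5 |
| 0 | 0.2 | 10 to 21 | about 38 |
| 0 | 0.4 | 34 to 80 | 97 |
| 0.2 | 0.2 | 82 to 99.8 | about 38 |

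The ranges run over σb = 0.8 to 0.4 mm. Compare the second and last rows: adding effect variation as large as the target difference barely moves the intercept test. It mainly reports level.

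**The case against.** The strongest defence is that Center Effects speaks of variability between centres, for which an intercept variance is a legitimate summary, and that effectiveness appears only at the last step, qualified as potential. That stands as a reading of the early sentences. It does not explain why a level variance should decide whether that last step is reached.

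Several stronger readings are tempting, and the protocol does not support them:
- *A significant variance test creates the subgroups.* It does not. The variability must also be clinically meaningful, covariates must identify meaningful groupings, and the subgroups must be large enough. The percentages above concern the significance test alone. The size that is judged is, however, still that of the intercept variance.
- *The plan would reach a wrong conclusion about heterogeneity.* This does not follow. The subgroup analyses repeat the primary model and would estimate the arm effect within each subgroup. Starting the search needlessly costs extra secondary analyses.
- *Real effect variation would mostly be missed.* The 10% to 21% figure assumes no level differences at all. With both kinds present the test is usually significant and the search goes ahead. The defect is lack of specificity.

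Two further points carry some weight. Primary Outcome Analysis says the levels can be represented by intercepts, and it lists random coefficients regression as another name for the model, so an unseen SAP might add a slope. But section 4.2 states the intercept firmly, and no treatment coefficient is described as random. The bootstrap will show the distribution of treatment effects across resamples, which is a partial safeguard but not an estimate of between-practitioner variation.

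**Conclusion.** The concern holds in this limited form. The stated step measures differences in probing-depth level and is non-specific for differences in the AMXM effect. This follows from the model structure and needs no assumed number. The size does: under the assumptions above, a constant AMXM effect gives a significant intercept test in about 20% to 55%, 78% to 99.6% and 99% to 100% of trials at level SDs of 0.1, 0.2 and 0.3 mm. The protocol supplies no practitioner or between-patient SD, so these percentages illustrate direction only.

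The consequence is confined to exploratory and secondary analyses. A reader might infer that the primary comparison is compromised; it is not, because its estimate, test and alpha do not depend on this step. The change is worth making because it is cheap and serves the trial's stated aim, but it is not critical.

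**What to change.** In Center Effects, add a supportive model with a practitioner-level random slope for arm-by-time (or a practitioner-by-arm-by-time interaction). Base three things on that term: the estimate of effect heterogeneity with its confidence interval, the variance test, and the decision to look for site subgroups. Report the intercept variance only as a description of level differences between practitioners. Keep the existing further conditions (clinically meaningful size, covariates that identify groupings, adequate subgroup size).

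The cost is one extra supportive model and a few sentences of wording; the primary analysis stays as it is. Power will be modest: about 38% for an effect SD of 0.2 mm with full follow-up, and about 28% with 6 patients per arm per practitioner. The interval should therefore carry the interpretation, and a non-significant result should not be read as a uniform effect.

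### Practice subgroups derived from the trial data are tested like the primary analysis at two-sided 0.05 and called secondary, with no interaction test required

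*Protocol*

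**What the plan says.** The Center Effects paragraph of Protocol 12.4 sets out a conditional chain.

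- **Trigger.** The variance of the centre random effect is tested and its size judged. The chain continues as follows: "If a clinically meaningful amount of variability between centers is detected". No threshold is given.
- **Search.** Then "exploratory analyses will be conducted to attempt to identify covariates related to center effects including" geographic, demographic and disease-related information. The list is open, and this is the only step called exploratory.
- **Subgroups.** If the search finds meaningful groupings, "subgroups of sites will be created based on the potential for differential effectiveness".
- **Tests.** "These subgroup analyses will be considered secondary and will be conducted in a manner identical to the primary analysis", with one limit: "provided that the subgroups are of sufficient size to merit such an analysis". Neither the size nor what counts as meaningful is defined.

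Three other statements in 12.4 decide what those tests are. On error level: "All statistical tests will be evaluated using a two-tailed alpha level of .05". On what counts as a result: "Significance of either interaction term will represent a difference between the treatment and control arm at that timepoint", so each subgroup has two chances, at 6 weeks and at 12 months. On the random effects for site, participant and practitioner: "each of which can be represented within the model by a random intercept".

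For its pre-specified subgroups (age, sex, race and ethnicity), the Key Subgroup Analyses paragraph adds a treatment-by-subgroup interaction to the model, and a significant interaction is the evidence for a difference in effect.

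**The concern.** The same outcome data may both suggest the practice subgroups and test them, and nothing stated for those tests allows for this: no hold-out data, no adjustment, no interaction test and no exploratory label. Data-derived subgroups need more caution than pre-specified ones, yet here they get less. A reader who sees a significant within-subgroup result reported as secondary, from the primary model, would take the nominal 0.05 at face value.

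At stake is a false statement that the antibiotics work in some kinds of practice. That matters in a trial whose rationale (Protocol 2.1 and 2.2) is to identify who benefits and to limit unnecessary antibiotic use.

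**Working it through.** The plan states no error rate for this step, so there is no figure of its own to reproduce. The checks below assume no treatment effect in any practice.

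**Inputs from the protocol.** 34 practitioners with a target of 16 participants each (34 × 16 = 544); 1:1 allocation in blocks within practitioner; two-sided 0.05; two follow-up timepoints, either of which counts; 220 per arm for 90% power at 0.2 mm.

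**Inputs assumed.** Two equal subgroups of 17 practices; the number K of candidate covariates; a correlation of 0.5 between timepoints; for the two-timepoint runs, a centre-intercept SD of 0.3 mm and 13 analysed participants per practice (16 × 0.8 = 12.8).

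**1. Multiplicity alone.** The two subgroups contain different participants, so their tests are independent.
- One timepoint: 1 − 0.95² = 0.0975.
- Two timepoints, if these were also independent: 1 − 0.95⁴ = 0.185.

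**2. Effect of how the split is chosen, one timepoint.** 20,000 null replicates of 34 standard-normal practice effects; K random 17/17 splits; the split with the largest difference is kept; the event is either subgroup with |z| > 1.96.

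| K | Chosen on practice intercepts | Chosen on observed treatment effects |
|---|---|---|
| 1 | 10% | 10% |
| 3 | 10% | 20% |
| 5 | 10% | 28% |
| 10 | 10% | 40% |

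Under the intercept rule each single test stays at about 5%. Blocked 1:1 allocation within practitioner makes a practice's intercept nearly independent of its treatment contrast.

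**3. Both timepoints.** 8,000 null replicates, four subgroup tests. For comparison, the whole-trial analysis gives about 9% over its two timepoints.
- Intercept rule: 17-18% for K from 1 to 20 (15-18% at K = 10 with timepoint correlations of 0.3 and 0.8).
- Treatment-effect rule: 40%, 53% and 64% for K = 5, 10 and 20.

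**4. A crude gate.** Suppose subgroups are formed only if the best covariate reaches p<0.05. The overall chance, over both timepoints with K = 5, 10 and 20, becomes 4%, 7% and 11% under the intercept rule and 16%, 29% and 47% under the treatment-effect rule. Among trials that do form subgroups it is about 17% and 73-75% respectively.

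**5. Bias under the treatment-effect rule.** The person-level SD implied by the sample size is 0.2 × √[220 / (2 × (1.960 + 1.282)²)] = 0.647 mm. The standard error of the overall difference is then 0.647 × √(2/220) = 0.062 mm, and in half the practices it is 0.062 × √2 = 0.087 mm. With no true effect, the better-looking subgroup shows on average 0.05 mm in favour of antibiotics with no search, which is simply the better of two. With 3 to 10 candidates searched it shows 0.08 to 0.11 mm, against the 0.2 mm that Protocol 12.2 calls clinically meaningful.

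**The case against.** The strongest reply is that the larger figures model a rule the protocol does not state. The search is for covariates related to centre effects, and in the primary model these are random intercepts: a practice's level of probing depth, not its treatment effect. On that reading the error does not grow with the number of covariates searched, each within-subgroup p-value keeps its nominal level, and selection adds no bias. What remains is ordinary multiplicity. This stands. A reader might infer that the growing error and the bias follow whatever variance triggers the search; they do not. They depend on reading the phrase about potential for differential effectiveness as observed effects, when it could also mean clinical plausibility.

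Second, the chain has gates: a variance test, a judgement of clinical importance, meaningful groupings and sufficient size. This stands too. The tabulated rates apply once subgroups are formed and are not the plan's overall error rate. But the gates other than the variance test have no threshold, and no gate protects the tests that follow.

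Third, a reader might infer that these subgroups rank equally with the pre-specified secondary outcomes, or that the plan lets them rescue a null trial. Neither is stated. The protocol uses the word secondary loosely, also for its effect-modification analyses, and its primary hypothesis concerns the whole trial.

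Fourth, a statistical analysis plan may settle candidate covariates and inferential status. It may add detail, but the protocol already fixes the label and the method for these subgroups.

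**Conclusion.** The point holds in limited form. The protocol has data-derived practice subgroups tested like the primary analysis at 0.05 under the label secondary, without the interaction test it requires of pre-specified subgroups.

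On the reading most favourable to the plan, the false-positive chance once two subgroups are formed is about 10% per timepoint and 17-18% over both, against about 5% and 9% for the whole-trial analysis. On the other reading it is about 20-40% per timepoint with 3 to 10 candidate covariates, with an exaggerated effect in the selected subgroup. The text does not settle which reading applies, so the larger figures are conditional.

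The sizes rest on two equal subgroups, an assumed number of covariates and an assumed correlation between timepoints. The analysis may never be triggered, and the trial-wide primary test is unaffected. It is still worth correcting before unblinding, because the change is small.

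**What to change.** In Protocol 12.4, Center Effects:

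1. Describe the practice-subgroup analyses as exploratory and hypothesis-generating instead of secondary.
2. Replace the re-run of the primary test within each subgroup by a treatment-by-practice-characteristic interaction, as in Key Subgroup Analyses, reported as an estimate with its 95% CI.
3. State that no within-subgroup significance claim will be made for subgroups derived from the data.
4. Optionally, report shrunken practice-specific treatment effects. The primary model has only random intercepts, so this needs a separate exploratory model with a random treatment slope by practitioner.

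Items 1 to 3 are changes of wording in one paragraph; item 4 costs one extra model. The downside is that no p-value can be claimed for a subset of practices. Splitting alpha instead (0.05 / 4 = 0.0125 for two subgroups and two timepoints) would deal with the multiplicity but not with selection on observed effects.
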